### ***2-point profile (SMPG) values used for dose adjustment***

The endpoints from the SMPG measurements obtained throughout the trial for dose adjustment will be:

- Mean PG before meals (breakfast and main evening meal) after 26 weeks of treatment
- Responder for PG titration targets
- Time from randomisation (measured in weeks) to achieve titration targets
- Within-subject variability as measured by CV% after 26 weeks of treatment

The mean PG value before a meal will be calculated at each visit using the available data and separately for breakfast and main evening meal.

The mean before meal PG values after 26 weeks of treatment will be analysed separately, using an ANOVA method with treatment, anti-diabetic therapy at screening and sex as fixed factors, and age and the corresponding mean PG value at baseline as covariates.

From the mean before meal PG value, a dichotomous endpoint (responder/non-responder) will be derived for each meal that shows if a subject has achieved the titration target at each visit.

For each target a survival endpoint will be derived as the time from randomisation to the date a subject achieves the titration target for the first time.

The two survival endpoints will be analysed separately in a Cox proportional hazards model including treatment, anti-diabetic therapy at screening and sex as fixed factors and age as covariate. An analysis will also be performed for the time to all titration targets are met. Subjects that are lost for follow up without meeting the target and subjects that never meet the target during treatment will be censored at the last day of treatment.

The logarithm transformed SMPG values available before breakfast and main evening meal, will be analysed separately as repeated measures in a linear mixed model with treatment, anti-diabetic therapy at screening and sex as fixed factors, age as covariate and subject as random factor. The model will assume independent within- and between-subject errors with variances depending on treatment. Within-subject variability as measured by CV% for a treatment can be calculated from the corresponding residual variance  $\sigma^2$  as  $CV\% = 100\sqrt{(\exp(\sigma^2)-1)}$ . The confidence interval for the CV ratio between treatments will be calculated using the delta method.

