## 6 Trial population

### 6.1 Number of subjects

Country planned to participate: China

Number of subjects planned to be screened (i.e. documented informed consent): 767

Number of subjects planned to be randomised/started on trial product(s): 537

Number of subjects expected to complete the trial: 450

A screening failure rate of 30 % and a withdrawal rate of 15% is anticipated for this trial.

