#### **6.4 Withdrawal criteria**

The subject may withdraw at will at any time.

The subject may be withdrawn from the trial at the discretion of the investigator due to a safety concern or if judged non-compliant with trial procedures.

Subjects randomised in error (not fulfilling the inclusion and/or exclusion criteria) must be withdrawn from the trial.

A subject must be withdrawn if the following applies:

1. Hypoglycaemia during the treatment period posing a safety problem as judged by the investigator
2. Protocol deviation having influence on efficacy or safety data as judged by the investigator
3. Initiation or significant change of any systemic treatment which in the investigator's opinion could interfere with glucose metabolism (inhaled corticosteroids are allowed, pausing metformin treatment for a planned radiographic procedure including the use of iodine containing contrast material is allowed)

4. Pregnancy or intention of becoming pregnant
5. Use of a different antidiabetic treatment regimen during the treatment period than metformin including use of insulin secretagogues (sulfonylurea or glinide), dipeptidyl peptidase IV (DPP-IV) inhibitors,  $\alpha$ -glucosidase-inhibitors, thiazolidinediones (TZDs) or GLP-1 receptor agonists during the treatment period
6. Donation of blood or participation in other trials throughout the trial
7. Lack of effect: After week 12, if the subject has not had a reduction in HbA1c and has a pre-breakfast SMPG reading > 13.3 mmol/L (> 240 mg/dL) on three consecutive days despite appropriate dose adjustments. The subject should contact the investigator and come in for an unscheduled visit as soon as possible (within 2 weeks). The next scheduled visit should not be awaited. An FPG should be obtained and analysed by the central laboratory. If this FPG exceeds 13.3 mmol/L (>240 mg/dL) and no treatable intercurrent cause for the hyperglycaemia has been diagnosed, the subject must be withdrawn.
8. The subject does not tolerate the minimum dose of 4 Units daily (2U per injection) during 14 consecutive days

A withdrawn subject should be called in for Visit 28 and the follow-up FU 1 (Visit 29) procedures and an appointment for the 30 days follow-up Visit FU2 phone contact (P30) should be made as described in section 0 and 8.1.7.

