Only endpoints derived after 26 weeks of treatment will be analysed statistically. Missing values will be imputed using the Last Observation Carried Forward (LOCF) method. LOCF has been a standard approach in diabetes trials for many years, and was used as the primary analysis in all degludec phase 3a trials. LOCF is considered to be an appropriate method in the context of treat-to-target trials, where subjects after withdrawal typically continue their therapy using commercially available insulin. In previous treat-to-target trials with degludec LOCF has generally provided similar results to alternative methods to handle missing data, such as repeated measures models and completer analyses. In this trial, similar sensitivity analyses will be made to examine the robustness of the LOCF method. All endpoints will be summarised descriptively at each visit by treatment and in total using observed data. After 26 weeks of treatment, descriptive statistics will be presented based both on observed and LOCF imputed data. Endpoints that are analysed untransformed and

endpoints that are not formally analysed are summarised by the arithmetic mean, standard deviation (SD), median, and minimum and maximum value. Endpoints that are analysed log-transformed are summarised by the geometric mean, CV, median, minimum and maximum value.

LOCF imputed data will be used as the basis for plotting data if not otherwise specified.

Presentation of results from a statistical analysis will include the estimated mean treatment effects (least-squares means [LSMeans]) for absolute values and change from baseline if applicable. Estimated mean treatment differences (or ratios) will be presented together with two-sided 95% confidence intervals for all endpoints analysed statistically. p-values will only be presented for the primary and the confirmatory secondary endpoints for which formal statistical testing will be performed. The other endpoints are considered supportive and explorative in nature and no p-values will be presented.

For endpoints measured over time mean values will be plotted to explore the trajectory over time. For survival endpoints, Kaplan-Meier plots are presented for each treatment. Data collected before randomisation will only be summarised descriptively.

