A mixed effect model will be fitted to the 9-point profile (SMPG) data. The model will include treatment, time, interaction between treatment and time, anti-diabetic therapy at screening and sex as fixed factors, age and the values from the profile at baseline as covariates and subject as random effect. From the model, mean profile by treatment and relevant treatment differences will be estimated and explored.

Mean and fluctuation in the 9-point profile (SMPG) and prandial PG increment endpoints will be analysed separately using an ANOVA method with treatment, anti-diabetic therapy at screening and sex as fixed factors, and age and the relevant baseline value as covariates. Fluctuation in the 9-point profile (SMPG) will be logarithm transformed before analysed.

2-point profile (SMPG) values used for dose adjustment

The endpoints from the SMPG measurements obtained throughout the trial for dose adjustment will be:

- Mean PG before meals (breakfast and main evening meal) after 26 weeks of treatment
- Responder for PG titration targets
- Time from randomisation (measured in weeks) to achieve titration targets
- Within-subject variability as measured by CV% after 26 weeks of treatment

The mean PG value before a meal will be calculated at each visit using the available data and separately for breakfast and main evening meal.

The mean before meal PG values after 26 weeks of treatment will be analysed separately, using an ANOVA method with treatment, anti-diabetic therapy at screening and sex as fixed factors, and age as covariates.

From the mean before meal PG value, a dichotomous endpoint (responder/non-responder) will be derived for each meal that shows if a subject has achieved the titration target at each visit.

For each target a survival endpoint will be derived as the time from randomisation to the date a subject achieves the titration target for the first time.

The two survival endpoints will be analysed separately in a Cox proportional hazards model including treatment, anti-diabetic therapy at screening and sex as fixed factors and age as covariate. An analysis will also be performed for the time to all titration targets are met. Subjects that are lost

for follow up without meeting the target and subjects that never meet the target during treatment will be censored at the last day of treatment.

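### Kaplan-Meier curves for time to titration target will read higher than the share of subjects who reached target on trial insulin, because stopping treatment early is handled as censoring

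*Protocol*

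**What the plan says.** Protocol 17.4.2.1 (2-point SMPG profile) defines, for each pre-meal target, "the time from randomisation to the date a subject achieves the titration target for the first time". SAP 2.4.2.1 uses the same definition. A further analysis covers the time until all targets are met, so three time-to-event endpoints are involved.

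On censoring, the protocol says: "Subjects that are lost for follow up without meeting the target and subjects that never meet the target during treatment will be censored". The censoring date is the last day of treatment. The SAP repeats the rule. Subjects who are lost, who withdraw or who complete without reaching target are all handled alike.

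On display, Protocol 17 and SAP 2 say: "For survival endpoints, Kaplan-Meier plots are presented for each treatment". On analysis: "The two survival endpoints will be analysed separately in a Cox proportional hazards model". Neither document names a competing event or a cumulative incidence method.

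On stopping, Protocol 6.1 says that "a withdrawal rate of 15% is anticipated for this trial". Protocol 5.3.1 and 8.1.7 move a subject who stops early to another insulin and to the end-of-treatment and follow-up procedures. One mandatory reason for withdrawal in Protocol 6.4 is lack of effect. It applies after week 12 to a subject who has had no HbA1c reduction and "has a pre-breakfast SMPG reading > 13.3 mmol/L" on three consecutive days, with a confirming central-laboratory value.

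**The concern.** The event can occur only while the subject takes trial insulin and records the 2-point profile. Stopping early therefore does more than hide a later event: it rules the event out, which makes it a competing event.

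Kaplan-Meier handles a censored subject as if that subject would go on to reach target at the rate of those still under titration. The resulting curve describes attainment had nobody stopped, and does so only if stopping is unrelated to the prospect of reaching target. For lack-of-effect withdrawals that condition is doubtful by the definition of the criterion.

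Both documents base the analysis of all endpoints on the full analysis set, with the intention-to-treat principle. Many readers will therefore take the height of the curve at week 26 as the share of randomised subjects who reached target. For that quantity the curve is too high in both arms, and by more in an arm that loses more subjects.

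**Working it through.** **Plan's own figure.** The documents give none for this endpoint. The one usable input is the withdrawal rate d = 15% over 26 weeks (Protocol 6.1). The same section expects 450 completers of 537, which gives 1 - 450/537 = 16.2%, close to the stated rate.

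**Assumptions not in the documents.** Attainment p, read as 1-KM at week 26, is varied from 30% to 90%. Withdrawal is 15% in each arm, at the same rate before and after target. Hazards are constant in the main case.

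**Formula.** Let a = -ln(1-p) and b = -ln(1-d). With constant hazards the 26 weeks cancel:

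share reaching target on treatment (CIF) = a/(a+b) × [1 - (1-p)(1-d)]

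share stopping before target = b/(a+b) × [1 - (1-p)(1-d)]

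**Worked example.** For p = 0.60 and d = 0.15: a = 0.916, b = 0.163, a/(a+b) = 0.849, and 1 - 0.40 × 0.85 = 0.66. CIF = 0.849 × 0.66 = 56.1%. The excess is 60 - 56.1 = 3.9 points.

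| 1-KM | CIF | Excess (points) | Stopped before target |
|---|---|---|---|
| 30% | 27.8% | 2.2 | 12.7% |
| 50% | 46.6% | 3.4 | 10.9% |
| 70% | 65.6% | 4.4 | 8.9% |
| 90% | 85.5% | 4.5 | 6.0% |

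The maximum is 4.6 points, at p of about 84%. With 16.2% withdrawal the maximum is about 5.0. At p = 70%, Kaplan-Meier in effect counts about half of the early stoppers (4.4 of 8.9) as later successes. The excess falls below 2 points when p is under about 27%.

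**Timing.** A weekly version of the calculation keeps 15% withdrawal and p from 30% to 90%:

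| Attainment | Withdrawal | Excess (points) |
|---|---|---|
| even | even | 2.1-4.3 |
| even | after week 12 only | 1.0-1.7 |
| even | mostly weeks 1-8 | 3.0-6.9 |
| mostly weeks 1-12 | even | 1.4-2.7 |
| mostly weeks 1-12 | after week 12 only | 0.4-0.6 |
| mostly weeks 1-12 | mostly weeks 1-8 | 2.3-5.0 |

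The first row is slightly below the constant-hazard result because the weekly version counts attainment before withdrawal within each week.

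**Lack of effect alone.** If 1-5% of subjects (assumed) withdraw for this reason, all after week 12, and attainment is even, the excess is about 0.1 to 0.6 points.

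**Between arms.** Take 60% versus 50% by Kaplan-Meier, a 10.0-point contrast. With 15% withdrawal in both arms the CIF contrast is 56.1 - 46.6 = 9.5 points. With 12% withdrawal in the 60% arm and 18% in the 50% arm it is 11.0; with the two rates exchanged it is 8.0. As an illustration only, two arms with the same 60% Kaplan-Meier value but 10% and 25% withdrawal have CIFs of 57.4% and 53.3%, a 4-point difference that the curves would not show.

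**The case against.** The strongest reply is that the documents never say that 1-KM will be reported as the share reaching target. The endpoint is a time, its analysis is a Cox model, and the result is supportive, without p-values. If the curve is read as attainment had everyone stayed on treatment, uninformative withdrawal does not bias it; only informative withdrawal does, by an unknown amount. The documents choose neither reading. This stands, and it is why the point is conditional on how the curve is read.

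A second reply is that proportions at target have their own endpoint, a responder variable for each meal and visit. This helps only in part. It gives status at a visit, not whether a subject ever reached target, so the cumulative share can be read only from the Kaplan-Meier plot.

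Three stronger readings are tempting, and the documents do not support them:

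- A reader might infer that the plan overstates attainment by a fixed 2 to 5 points. That needs attainment, timing and per-arm withdrawal figures that are not given.
- A reader might infer that withdrawal for lack of effect or hypoglycaemia drives the excess because such subjects could not be brought to target. Lack of effect contributes little in the calculation above. Some subjects withdrawn for hypoglycaemia may already have met the target, and reasons such as pregnancy or blood donation say nothing about it.
- A reader might infer that the treatment comparison is invalid. The Cox model still estimates a cause-specific hazard ratio under this censoring, and with equal withdrawal the contrast in proportions hardly moves. The open-label design makes unequal withdrawal possible, but the documents give no split by arm.

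It is also fair to object that counting loss to follow-up as a competing event assumes that the subject did not reach target, when the outcome may be unknown. The fix allows for this.

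**Conclusion.** The point holds as a matter of display and interpretation. Early stopping rules out the event, the plan censors it, and 1-KM therefore exceeds the share of randomised subjects who reached target on trial insulin. The direction follows from the rules. The size does not: 2.2 to 4.6 points needs 15% withdrawal in each arm, constant hazards and 30-90% attainment, and changing only the timing gives about 0.4 to 6.9. If subjects not yet at target stop more often than those who have reached it, the excess would be larger for the same overall withdrawal. No confirmatory result is affected. The hazard ratio needs a label but no re-analysis. The priority is low.

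**What to change.** In Protocol 17.4.2.1 and SAP 2.4.2.1, for the three time-to-target endpoints:

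- Add Aalen-Johansen cumulative incidence curves per arm beside the Kaplan-Meier plots. Use discontinuation of trial insulin before target as the competing event, and report week-26 proportions with 95% confidence intervals. Censor only subjects who complete treatment without reaching target.
- State that subjects lost to follow-up count as not having reached target on trial insulin, or show them censored in a sensitivity display.
- Keep the Cox model and label its result a cause-specific hazard ratio.

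The Kaplan-Meier plots need not be removed. The required data (last treatment date, reason for withdrawal and SMPG values) are already collected under Protocol 8.1.3, 8.1.7 and 8.4. The cost is a few lines of SAP text and slightly more output. The shares reported at target will be somewhat lower than the Kaplan-Meier plots alone would suggest.

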#### **17.4.2.2 Safety**

##### **Adverse Events**

Adverse Events will be coded using the most recent version of Medical Dictionary for Regulatory Activities (MedDRA) coding. All AEs will be presented based on system organ class and preferred terms.

When reporting the trial results the EAC evaluation will be employed. All discrepancies between EAC and the investigators' classification of the CV events will be listed by event.

A Treatment Emergent Adverse Event (TEAE) is defined as an event that has onset date on or after the first day of exposure to randomised treatment and no later than 7 days after the last day of randomised treatment.

TEAEs are summarised descriptively whereas AEs not defined as treatment emergent are presented in listings. The summaries of TEAEs are made displaying the number of subjects with at least one event, the percentage of subjects with at least one event, the number of events and the event rate per 100 years. These summaries are done by seriousness, severity, relation to insulin treatment, relation to device, withdrawal due to AEs and outcome.

Furthermore summary tables based on system organ class and preferred terms are made for:

- all TEAEs
- serious TEAEs
- possibly or probably related TEAEs
- severe TEAEs
- TEAEs with preferred term that are experienced by at least 5% of the subjects in any treatment arm or by at least 5% of all subjects

### **Hypoglycaemic episodes**

Hypoglycaemic episodes are recorded by subjects in their trial diaries throughout the trial. The information collected includes PG before treating the episode and whether the subject was able to treat him/herself. This information is used by Novo Nordisk A/S to classify an episode according to the confirmed hypoglycaemia definition and the ADA definition (severe, documented symptomatic, asymptomatic, probable symptomatic and relative) as further detailed in section [8.8](#).

A hypoglycaemic episode is defined as treatment emergent if the onset of the episode is on or after the first day of exposure to randomised treatment and no later than 7 days after the last day of randomised treatment. A hypoglycaemic episode that has time of onset between 00:01 and 05:59 a.m. (both included) is considered to be nocturnal.

Data on treatment emergent hypoglycaemic episodes are presented in terms of the number of subjects with at least one event (N), the percentage of subjects with at least one event (%), the number of events (E) and the event rate per 100 years (R). Separate summaries are made by severity considering all confirmed hypoglycaemic episodes, confirmed hypoglycaemic episodes in the maintenance period, nocturnal confirmed hypoglycaemic episodes, nocturnal confirmed hypoglycaemic episodes in the maintenance period and the ADA classification of hypoglycaemia.

The number of treatment emergent severe, confirmed, confirmed in the maintenance period, nocturnal confirmed hypoglycaemic episodes and nocturnal confirmed in the maintenance period will be analysed using a negative binomial regression model with a log-link function and the logarithm of the time period for which a hypoglycaemic episode is considered treatment emergent as offset. The model will include treatment, anti-diabetic therapy at screening and sex as fixed factors, and age as covariate. If the number of severe or nocturnal confirmed hypoglycaemic episodes is too small for statistical analysis, then these analyses may not be performed.

### **Fundoscopy/fundus photography**

Fundoscopy and fundus photography findings will be summarised descriptively including summaries of the change from baseline.

## **ECG**

ECG 12-lead findings will be summarised descriptively including summaries of the change from baseline.

## **Physical examination**

Physical examination should include:

- head, ears, eyes, nose, throat, neck
- respiratory system
- CV system
- gastrointestinal system incl. mouth
- musculoskeletal system
- central and peripheral nervous system
- skin

The physical examination measurements and their change from baseline will be summarised descriptively.

## **Vital signs**

Vital signs include diastolic blood pressure, systolic blood pressure and pulse findings will be summarised descriptively including summaries of the change from baseline.

## **Laboratory safety parameters**

The following laboratory assessments are performed:

- haematology (haemoglobin, leucocytes, thrombocytes, haematocrit, differential counts and erythrocytes)
- biochemistry (creatinine, total protein, ALT, AST, AP, sodium, potassium, albumin, total bilirubin)
- lipid profile (LDL, HDL, triglycerides and total cholesterol)
- urinary albumin-to-creatinine ratio assess in spot urine
- urine by sticks (tests for blood, protein and ketones)
- insulin antibodies

Individual laboratory values will be compared to their relevant reference range (when existing) and flagged as being below or above the range. Change from baseline will be summarised descriptively.

Change from baseline in lipid endpoints after 26 weeks of treatment will be analysed separately using an ANOVA method with treatment, anti-diabetic therapy at screening and sex as fixed factors, and age and baseline value as covariates.

Insulin degludec specific antibodies, insulin aspart specific antibodies, and cross-reacting antibodies will be illustrated using descriptive statistics and graphs.

### **Insulin dose**

Prescribed and actual insulin dose per day and separately for morning and evening dose will be recorded. The respective insulin doses will be summarised descriptively according to regimen as dose in units and units/kg per week.

